6.5.5. Physical Examinations

A complete PE includes evaluation of the head, eyes, ears, nose, and throat, and the cardiovascular, dermatological, musculoskeletal, respiratory, and gastrointestinal systems. Breast, genital, and rectal examinations are not required, unless warranted in the opinion of the health care provider. Limited examinations should include cardiovascular, respiratory, and gastrointestinal systems. Symptom-directed PEs may also include any other pertinent system as required. The examination will be performed by a physician or by a nurse practitioner or physician's assistant under the supervision of a physician.

Complete or limited or symptom-directed examinations will be performed at time points indicated in the Schedule of Assessments. For visits with study drug administration, this should be completed prior to the study drug infusion. Additional examinations may be completed as clinically indicated.

Record abnormalities observed at screening on the General Medical History and Baseline Conditions page of the eCRF. At subsequent visits, record new or worsened clinically significant abnormalities on the AE eCRF.

Height (cm) will be measured at screening.

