6.5.6. Neurological Examinations

A complete neurologic examination should include the evaluation of consciousness, orientation, cranial nerves, motor and sensory system, coordination and gait, and reflexes. Limited or symptom-directed examinations will be performed at all other specified time points. A symptom-directed neurological examination should focus on the affected organ system or body area.

For visits with study drug administration, this should be completed prior to study drug infusion. Additional examinations may be completed as clinically indicated.

Record abnormalities observed at screening on the General Medical History and Baseline Conditions page of the eCRF. At subsequent visits, record new or worsened clinically significant abnormalities as AEs on the AE eCRF.

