7.3. Eliciting and Documenting Adverse Events

At every study visit, participants will be asked a standard, nonleading question to elicit any medically related changes in their well-being. They will also be asked if they have been hospitalized, had any accidents, used any new medications, or changed concomitant medication regimens (prescription drugs, herbal products, vitamins, minerals, vaccines, topical medications, and over-the-counter medications).

Laboratory test values or investigational findings (e.g., findings on ECGs, imaging, or examination) outside the normal reference range that meets the following criteria should be reported as an AE: (1) is confirmed and the investigator considers clinically significant, or (2) requires a participant to be discontinued from the study, or (3) requires a participant to receive treatment. Abnormal laboratory test values or investigational findings reported as AEs

should be followed until satisfactory clinical resolution, participant withdrawal of consent, loss to follow-up, or death, whichever comes first.

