In most instances, study drug should be administered at the investigational site. In the event the participant is unable to have study drug administered at the investigational site (i.e., due to participant or site restrictions related to Covid-19) study drug administration for the third and subsequent infusions may be performed “at home” (i.e., at the participant’s home or other suitable location) by a home healthcare provider who has appropriate training and expertise in IV administration. Study drug administration for the first and second infusion must be conducted at the investigational site, at home study drug administration for subsequent infusions may only be performed with Medical Monitor approval.

The following procedures must be performed for each at home study drug administration:

Before study drug administration:

- Home healthcare provider will record vital signs, including systolic and diastolic BP, pulse, body temperature, and respiratory rate (recorded after the participant has been resting for at least 5 minutes in the supine position)
- Home healthcare provider will conduct an assessment^{1,2} to include evaluation of general appearance, skin, EENT, head and neck, extremities, abdomen, and respiratory, cardiovascular, neurological, and musculoskeletal systems
- Home healthcare provider will conduct a review of concomitant medication(s)
- Home healthcare provider will record any AEs (signs and symptoms) which may have occurred since previous visit
- Home healthcare provider will contact the investigative site by phone or video (investigator or designee) to review findings from the assessment, adverse events and concomitant medications
- Home healthcare provider must receive email confirmation from the investigative site to proceed with study drug administration, prior to initiating study drug administration.

During study drug administration:

- Approximately 15 and 45 minutes after initiating study drug administration, monitor vital signs, including systolic and diastolic BP, pulse, body temperature, and respiratory rate²
- Monitor for infusion-related reactions or injection-related reactions³
- Record any AEs (signs and symptoms)

After study drug administration

- Record vital signs, including systolic and diastolic BP, pulse, body temperature, and respiratory rate (recorded within 15 minutes after the end of infusion)
- Monitor for infusion-related reactions or injection-related reactions for at least 90 minutes post-infusion³

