- Conduct an assessment^{1,2} to include evaluation of general appearance, skin, EENT, head and neck, extremities, abdomen, and respiratory, cardiovascular, neurological, and musculoskeletal systems
- Record any AEs (signs and symptoms)

If any AEs are observed during or after study drug administration the home healthcare provider must contact the clinical site by phone or video (investigator or designee) to review findings and to take appropriate action(s), if directed by the investigator (or designee).

If required, the site investigator may also conduct a tele visit prior to, during, or after study drug administration.

¹ The assessment will substitute for the protocol specified physical and neurological examination .

² Abnormalities identified during the assessment should be recorded as an AE and reported to the site in order to be entered in the EDC.

³ Management of infusion-related and/or injection-related reactions is described in Protocol [Section 5.1.2](#).

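### The AE recording rule for examination findings is looser at home infusions than at site visits, so AE counts depend partly on where the drug was given

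*Protocol*

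**What the plan says.** **Home infusions.** Protocol Appendix 3 (At Home Study Drug Administration) allows the third and later infusions at home, with Medical Monitor approval. The provider carries out a body-system assessment, including the neurological system, before and after the infusion. Both are tagged with footnotes 1 and 2. Footnote 1: "The assessment will substitute for the protocol specified physical and neurological examination". Footnote 2: "Abnormalities identified during the assessment should be recorded as an AE and reported to the site", for entry in the EDC. The in-infusion instruction, "Approximately 15 and 45 minutes after initiating study drug administration, monitor vital signs", also carries footnote 2.

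**Site visits.** Section 6.5.5, on physical examinations: "At subsequent visits, record new or worsened clinically significant abnormalities on the AE eCRF". Section 6.5.6, on neurological examinations: "At subsequent visits, record new or worsened clinically significant abnormalities as AEs on the AE eCRF". Section 6.5.7 applies the same test to vital signs. Section 7.3 makes an out-of-range finding an AE on any of three grounds. The first reads "1) is confirmed and the investigator considers clinically significant"; the others are that it requires discontinuation from the study or requires treatment.

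**Analysis.** Incidence, nature and severity of AEs is a primary endpoint in Part 1 (protocol Table 1) and Part 2 (Table 2). SAP Sections 6.5 and 12 drop the examination summaries and listings, because results are entered only on the medical-history and AE pages. SAP Section 6.1 reports participants and number of events; SAP Section 2 presents summaries by cohort and overall. No summary is by place of infusion.

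**The concern.** Footnote 1 gives the home assessment the role of the site examination, but footnote 2 gives it a different recording rule. It omits the qualifiers new or worsened and clinically significant. Nothing in Appendix 3 makes it subject to Sections 6.5 or 7, although footnote 3 does refer the reader to Section 5.1.2 for its own topic.

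In an open-label, single-arm study whose primary result is descriptive AE incidence, one recording rule has to apply to everyone. If it does not, cohorts, sites or calendar periods with more home dosing can show more AEs for reasons unrelated to the drug. After baseline the AE page is the only route by which examination findings reach the analysis, so no separate examination table exists to reveal the artefact.

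**Working it through.** **1. The rules side by side, by type of finding.**

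| Finding | Site (6.5.5–6.5.7, 7.1, 7.3) | Home (footnote 2, read with 7.1) | Differs? |
|---|---|---|---|
| Present at screening, unchanged | Not an AE (7.1) | AE on the footnote's words alone; excluded by 7.1 and the TEAE definition | Should not, in TEAE tables |
| New or worsened, clinically significant | AE | AE | No |
| Requires treatment or discontinuation | AE (7.3) | AE | No |
| New (or worsened), not clinically significant, no treatment or discontinuation | Not recorded under 6.5.5–6.5.7 or 7.3 | AE | **Yes** |

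Only the last row separates the two settings. Such a finding meets the TEAE definition (SAP Section 6.1), because it was absent before exposure or has worsened, so it stays in the tables.

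**2. Opportunity to detect.** Each home infusion has 2 assessments plus vital signs at about 15 and 45 minutes. The site schedule has vital signs before the dose and at the end of infusion. Infusions eligible for home dosing number at most 25 − 2 = 23 in Part 1 and 50 − 2 = 48 over both parts. These are ceilings; actual use is not stated.

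**3. The plan's own figure.** Protocol Section 8.1 gives the chance of at least one clinically significant associated finding in 40 participants. The formula 1 − (1 − p)^40 at p = 0.1%, 1%, 5% and 10% gives 3.923%, 33.103%, 87.149% and 98.522%, which matches the stated 3.9%, 33.1%, 87.1% and 98.5%. That figure concerns clinically significant findings and is unaffected here.

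**4. Illustration of size (all inputs assumed).** Let q be the chance per home assessment of a finding of the last type and k the number of home infusions. Take 2 assessments per infusion, independence, and none recorded at the site; ignore the extra vital signs. The chance of at least one extra AE per participant is x = 1 − (1 − q)^(2k):

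| k | q = 1% | q = 5% |
|---|---|---|
| 1 | 2.0% | 9.8% |
| 3 | 5.9% | 26.5% |
| 6 | 11.4% | 46.0% |
| 23 (Part 1 ceiling) | 37.0% | 90.6% |

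For any-AE incidence, let b be the incidence under the site rule and h the share of participants with home infusions. Observed incidence is b + h(1 − b)x. With b = 60% and h = 25%:

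- q = 1%, k = 3: 0.60 + 0.25 × 0.40 × 0.059 = 60.6%, or 24.2 of 40 instead of 24.0.
- q = 5%, k = 12: x = 1 − 0.95^24 = 0.708, giving 0.60 + 0.25 × 0.40 × 0.708 = 67.1%, or 26.8 of 40.

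The expected extra event records among the 10 participants with home infusions are 10 × 2k × q: 10 × 6 × 0.01 = 0.6 in the first case and 10 × 24 × 0.05 = 12 in the second. Event counts therefore move more than participant incidence. Many participants already have some other AE, but each extra record still adds to the event column and can add to a SOC/PT row.

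**The case against.** **Section 7.1 and the TEAE definition already protect the tables.** This is right for stable pre-existing findings. A reader might infer that a symptomatic participant's standing neurological sign becomes a new AE at every home assessment, up to 23 × 2 = 46 records in Part 1 and 48 × 2 = 96 overall, against none at the site. The documents do not support that. Section 7.1 excludes pre-existing conditions that do not worsen, screening abnormalities are documented as baseline conditions, and SAP Section 6.1 counts a participant once for repeats of the same AE. The protection does not reach new findings that are not clinically significant.

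**The investigator is involved.** Appendix 3 requires phone or video review of the assessment findings with the investigator or designee before dosing, and further contact if AEs occur during or after infusion. It would be wrong to say that no judgement is applied, and footnote 2 may have been meant as an instruction to report to the site. Even so, no text lets the site leave out a finding that is not clinically significant, and the footnote's stated purpose is entry in the EDC.

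**The site rule is not so narrow.** Section 7.3 has no new-or-worsened test and adds the treatment and discontinuation grounds. Section 7 says to report in case of doubt, and Section 7.1 asks for AEs regardless of clinical significance. This narrows the gap. But those general statements apply in both places and do not explain a separate rule for home examination findings.

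**Home dosing is exceptional.** Appendix 3 is confined to pandemic circumstances, expects most infusions at the site and requires Medical Monitor approval. This limits the size of the effect without removing the inconsistency.

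**Conclusion.** The inconsistency is real and feeds the primary endpoint, but it is narrow. It concerns new (or worsened) findings that are not clinically significant and require neither treatment nor discontinuation. These would be AEs after a home assessment and generally not after a site examination. The effect falls mainly on event counts and SOC/PT rows, and less on the proportion of participants with any AE. Its direction is towards more recorded minor events where home dosing was more frequent.

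The size cannot be derived from the documents. The figures above depend on an assumed rate of minor findings, an assumed number of home infusions and independence between assessments. They range from about half a percentage point to 7 points on a 60% incidence, under the stated inputs. The stronger inference, that TEAE incidence climbs with every home visit because of stable disease signs, does not hold. No stated figure in the plan is wrong on this account.

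**What to change.** **Protocol.** Reconcile footnote 2 with Sections 6.5.5 to 6.5.7, 7.1 and 7.3. The home provider reports all findings to the site and they are kept in source. The investigator then decides which are AEs by the criteria used at site visits, including the treatment and discontinuation grounds in Section 7.3. Apply the same text to the 15- and 45-minute vital signs.

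**Data and SAP.** Flag the place of each infusion and add an AE summary by it. Before lock, query home-visit AE records for consistency (onset, whether pre-existing, clinical significance). Do not delete recorded AEs; the purpose is to characterise them.

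**Cost.** A short amendment, which under Section 12.4.1 goes to the IRB/IEC, plus one flag, one data-management query and one additional table. No safety information is lost, since every home finding still reaches the site and stays in source.

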aFTD- GRN	Asymptomatic frontotemporal dementia carriers heterozygous for granulin mutations
ALT	Alanine aminotransferase
ANC	Absolute neutrophils count
AST	Aspartate aminotransferase
ATC	Anatomical-Therapeutic-Chemical
AUC _{ss}	Area under the concentration-time curve at steady state
BP	Blood pressure
bvFTD	Behavioral variant frontotemporal dementia
CDR	Clinical Dementia Rating Scale
CGI-I	Clinical Global Impression of Improvement
CGI-S	Clinical Global Impression of Severity
CI	Confidence interval
C _{max}	Maximum observed concentration
CNS	Central nervous system
COA	Clinical outcome assessment
CSF	Cerebrospinal fluid
CSR	Clinical study report
C _{trough}	Trough concentration
CTT	Color Trails Test
CV	Coefficient of variation
D-KEFS	Delis-Kaplan Executive Function System
DTI	Diffusion tensor imaging
ECG	Electrocardiogram
eCRF	Electronic case report form
FCRS	Frontotemporal Dementia Clinical Rating Scale
FDA	US Food and Drug Administration
FRS	Frontotemporal Dementia Rating Scale
FTD	Frontotemporal dementia
FTD- C9orf72	Symptomatic frontotemporal dementia patients with C9orf72 hexanucleotide repeat expansion mutations
FTD- GRN	Symptomatic frontotemporal dementia patients heterozygous for granulin mutations
FTLD	Frontotemporal lobar degeneration
FTLD-FUS	Frontotemporal lobar degeneration – immunoreactive to the fused in sarcoma protein
FTLD-TDP	Frontotemporal lobar degeneration – transactive response DNA-binding protein 43
GCP	Good Clinical Practice
GRN	Granulin
ICF	Informed consent form
ICH	International Council for Harmonisation

IEC	Independent ethics committee
IRB	Institutional review board
IV	Intravenous
MedDRA	Medical Dictionary for Regulatory Activities
MMRM	Mixed model of repeated measures
MMSE	Mini-Mental Status Exam
MRI	Magnetic resonance imaging
mRNA	messenger ribonucleic acid
NFL	Neurofilament-light
NPI	Neuropsychiatric Inventory
OLE	Open-Label Extension
PD	Pharmacodynamic(s)
PE	Physical examination
PGRN	Progranulin
PK	Pharmacokinetic(s)
PPA	Primary progressive aphasia
PT	Preferred term
q4w	Every 4 weeks
QTcF	QT interval corrected using Fridericia formula
RBANS	Repeatable Battery for the Assessment of Neuropsychological Status
SAE	Serious adverse event
SAP	Statistical analysis plan
Sheehan-STS	Sheehan Suicidality Tracking Scale
SOC	System organ class
TDP-43	DNA-binding protein 43
TEAE	Treatment-emergent adverse event
ULN	Upper limit of normal
████████	████████
WBC	White blood cell
WGS	Whole genome sequencing
WHO	World Health Organization
WHO-DD	WHO Drug Dictionary
WLA	Winterlight Lab Speech Assessment
WOCBP	Woman of childbearing potential

1. Introduction

This document outlines the statistical methods to be implemented during the analysis of data collected within the scope of Alector Inc. protocol AL001-2 version 4.0, dated 04 Feb 2021 (A Phase 2, Multicenter, Open-Label Study to Evaluate the Safety, Tolerability, Pharmacokinetics, and Pharmacodynamics of AL001 in Heterozygous Carriers of Granulin or C9orf72 Mutations Causative of Frontotemporal Dementia) and the previous version 3.2 United Kingdom, dated 23 November 2020, version 3.1, dated 13 July 2020, version 3.0, dated 02 June 2020, version 2.0, dated 26 September 2019 and the original protocol version 1.0, dated 09 April 2019. The purpose of this plan is to provide specific guidelines for the analyses. Any deviations from these guidelines will be documented in the clinical study report (CSR). The analyses described in this plan are considered a priori, in that they have been defined prior to database lock. Any analyses performed subsequent to database lock will be considered post-hoc and exploratory post-hoc analyses will be identified in the CSR.

1.1. Objectives and Endpoints

Table 1: Part 1 (Treatment Period): Study Objectives and Endpoints

	Objective(s)	Endpoint(s)
Primary	The primary objective of the treatment period of the study is to evaluate the safety and tolerability of IV administration of AL001 over 96 weeks in asymptomatic and symptomatic carriers of a GRN mutation causative of FTD and in symptomatic carriers of a C9orf72 mutation causative of FTD.	Primary Safety Endpoints: To assess the potential effect of cumulative exposure on the safety profile of AL001, the following will be evaluated by dose, such as by using tertiles of the actual dose (normalized to weight) received: 
• Incidence, nature, and severity of AEs and SAEs• Incidence of treatment discontinuations and study discontinuations due to AEs• Physical examination abnormalities• Neurological examination abnormalities• Changes in vital signs from baseline over time• Changes in ECGs from baseline over time• MRI abnormalities after dosing relative to baseline• Changes in clinical laboratory tests from baseline over time• Sheehan Suicidality Tracking Scale (Sheehan-STS)• Incidence of ADAs to AL001
Secondary	The secondary objectives of the treatment period of the	

	
study are to evaluate the effect of IV administration of AL001 over 96 weeks in asymptomatic and symptomatic carriers of a GRN mutation causative of FTD and in symptomatic carriers of a C9orf72 mutation causative of FTD on the following:
	
	
Secondary PK Objective:
 
 • PK 	
Secondary PK Endpoints:
 
 • Serum concentration of AL001 at specified time points • AL001 PK parameters (if data permit) ◦ C_{max} ◦ C_{trough} ◦ AUC_{ss}
	
Secondary PD Biomarker Objectives:
 
 • Longitudinal plasma and CSF PGRN concentration levels • Longitudinal levels of Sortilin in WBCs 	
Secondary PD Biomarker Endpoints:
 
 • The overall change from baseline in PGRN in CSF • The overall change from baseline in PGRN in plasma • The overall change from baseline in Sortilin in WBCs in plasma
Exploratory	
The exploratory objectives of the treatment period of the study are to assess the effect of IV administration of AL001 over 96 weeks in asymptomatic and symptomatic carriers of a GRN mutation causative of FTD and in symptomatic carriers of a C9orf72 mutation causative of FTD on the following:
	
	
Exploratory PD Biomarker Objectives:
 
 • Longitudinal blood, plasma, and CSF concentration levels of exploratory biomarkers of neurodegeneration, lysosomal function, and glial activity • MRI measures to evaluate changes in the brain • Global and regional brain MRI atrophy measures 	
Exploratory PD Biomarker Endpoints:
 
 • The overall change from baseline in exploratory biomarkers of neurodegeneration, lysosomal function, and glial activity in blood, plasma, and CSF • Global and regional brain MRI atrophy measures • Correlations among exploratory fluid biomarkers, imaging measures, and COAs

	
 • Correlations among exploratory fluid PD biomarkers, imaging PD measures, and COAs 
Exploratory Clinical Objectives:
 
 • Clinical progression as measured by COAs 	
	
Exploratory Clinical Endpoints:
 
The overall change from baseline on the scores of the instruments in the COAs
 
 • Clinical Dementia Rating Dementia Staging Instrument PLUS National Alzheimer's Disease Coordinating Center Frontotemporal Lobar Degeneration Behavior and Language Domains (Clinical Dementia Rating (CDR®) plus NACC FTLD) • Frontotemporal Dementia Rating Scale (FRS) • Clinical Global Impression of Improvement (CGI-I) • Clinical Global Impression of Severity (CGI-S) • Color Trails Test (CTT) Part 2 • Repeatable Battery for the Assessment of Neuropsychological Status (RBANS) • Winterlight Labs Speech Assessments (WLA; for participants who agree to participate in these optional assessments only) 	

Table 2: Part 2 (Optional Open-Label Extension (OLE)): Objectives and Endpoints

	Objective(s)	Endpoint(s)
Primary	The primary objective of the OLE period of the study is to assess the long-term safety and tolerability of AL001 in participants who have completed 96 weeks of treatment on Part 1 of the study.	
 • Incidence, nature, and severity of AEs and SAEs • Incidence of treatment discontinuations and study discontinuations due to AEs • Physical examination abnormalities • Neurological examination abnormalities • Changes in vital signs from baseline over time • Changes in ECGs from baseline over time • MRI abnormalities after dosing relative to baseline • Changes in clinical laboratory tests from baseline over time • Sheehan-STS

		
 • Incidence of ADAs to AL001
Exploratory	
COAs, correlative assessments (e.g., biomarker) and other efficacy assessments conducted during the OLE are considered exploratory. The exploratory objectives of the OLE period of the study are to assess the long-term effect of AL001 in participants who have completed 96 weeks of treatment on Part 1 of the study on the following:
 
 • PK • Longitudinal plasma and CSF PGRN concentration levels • Longitudinal blood, plasma, and CSF concentration levels of exploratory biomarkers of neurodegeneration, lysosomal function, and glial activity • Magnetic resonance imaging (MRI) measures to evaluate changes in the brain 	
Serum concentration of AL001 at specified time points
 
 • AL001 PK parameters (if data permit) 
 ◦ C_{max} ◦ C_{trough} ◦ AUC_{ss} • The overall change from baseline in PGRN in plasma • The overall change from baseline in exploratory biomarkers of neurodegeneration, lysosomal function, and glial activity in blood, plasma, and CSF • Global and regional brain MRI atrophy measures
	
 • Correlations among exploratory fluid PD biomarkers, imaging PD measures, and clinical outcome assessments (COAs) 	
 • Correlations among exploratory fluid biomarkers, imaging measures, and COAs
	
 • Clinical progression as measured by COAs 	
The overall change from baseline on the scores of the instruments in the COAs
 
 • CDR® plus NACC FTLD • FRS • CGI-I • CGI-S • CTT Part 2 • RBANS

		
• Winterlight Labs Speech Assessments (for participants who agree to participate in these optional assessments only)
--	--	--

[figure not shown]
